Overview: In Aim 1, we will conduct at least five focus groups with PCPs and 8 individual interviews to learn their thoughts, attitudes, and experiences with discussing and estimating older adults' prognosis when recommending stopping cancer screening. In addition, we will conduct 30 semi-structured qualitative interviews with adults 76-89 years with approximately 5-10 year life expectancy to learn their thoughts, feelings, and experiences with respect to discussing their prognosis with their PCPs. In addition, we will attempt to interview 5 financial planners and 5 members of the clergy to learn their approach to talking about life expectancy with older adults and the language that they use. We will use data gleaned from these interviews to develop strategies and guiding principles for PCPs to discuss prognosis with their patients when discussing stopping cancer screening and we will draft scripts to suggest language for PCPs to use when having these discussions. Focus groups will be held in an available conference room at BIDMC. Individual interviews will be held in a place that is convenient for the individual, such as available conference room, private office, or private clinic space at BIDMC, or at the patient's home or other private space. In Aim 2, we will learn if PCPs find the scripts and information on their patients' prognosis useful. We will give 45 PCPs (23 community-based) the scripts and patient prognostic information (using the Lee/[name] index and the Walter et al. life expectancy tables) on 1-3 of their patients (goal to recruit 100 patients overall). We will interview PCPs after each patient visit to learn if they found the prognostic information helpful and for feedback on the scripts. We will interview patients after each visit to learn from their perspective if their PCP discussed their prognosis and/or stopping cancer screening and to learn patients' thoughts on these discussions. We will also review the PCP note from the visit to learn if any discussion about prognosis or cancer screening was documented. These data are needed to help PCPs feel prepared to discuss stopping cancer screening and patient prognosis with older adults with <10 year life expectancy.

Aim 1- To learn from PCPs and older adults about how to discuss patient prognosis when recommending stopping cancer screening and to develop strategies for having these discussions.

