PCP recruitment: We will recruit PCPs from the same practices and using the same methods as in Aim 1. PCPs that participate in Aim 1 will be permitted to participate in Aim 2 since we will now be obtaining data from PCPs based on their experience at the point of care. We will explain to PCPs that we are interested in learning strategies for talking to older adults about stopping cancer screening and that we will attempt to recruit up to 5 of their patients to participate. Once one of their patients agrees to participate, we will send the PCP via secure email the patient's prognosis calculated by the Lee-[name] index three days before the patient visit. We will also send PCPs information on patient life expectancy from Cho et al.'s US life tables (see Appendix A9 for an example).⁷⁵ In addition, we will send PCPs the scripts we develop in Aim 1 on how to sensitively include information on patient prognosis when recommending patients stop being screened for cancer. After three of their patients have participated or once we meet our recruitment goals, we will ask PCPs to complete a 10 minute web-based questionnaire about their experience (details below).. We will also offer PCPs to complete questionnaires in person or over the phone if they prefer. We will provide PCPs a \$75 incentive. We aim to have 45 PCPs (1/3 community-based) participate.

Patient recruitment: Patient eligibility criteria and recruitment methods are the same as in Aim 1 except we will only recruit patients with a routine visit scheduled in the next 3-12 weeks with a participating PCP. We will obtain verbal rather than written consent for Aim 2 because we do not plan to audiotape interviews. Also, we will exclude patients that participated in Aim 1. Briefly, we will send patients deemed eligible by their PCP an informational letter about the study. The RA will call patients that do not opt-out of being contacted to reassess patient eligibility and willingness to participate. For patients willing and eligible to participate, the RA will schedule a time to administer the background questionnaire (Table 2 below) before the patient sees his/her PCP. Within 3 days of the PCP visit, the RA will administer a follow-up questionnaire. Patients will receive \$25 incentive for participating. More details on patient recruitment for Aim 2 are in Human Subjects, section E.2.a.

Table 2: Data Collection	When	Content

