Patient Background Questionnaire (Appendix A2)	RA administers before visit	Assesses: race/ethnicity, education, sociodemographics, ⁹⁰ function, ⁹¹ life expectancy (Lee-[name] index), ^{28, 92} comorbidity, ⁷³ family history of cancer, and intentions to be screened for breast (women only) and CRC cancer (all), ⁹³ patient perceived trust in their PCP
Patient Follow-up Questionnaire (Appendix A6)	RA administers within 3 days of the visit	- Whether PCP talked about stopping cancer screening and/or patient life expectancy If so were they satisfied with the information, how did it make them feel, feedback? If not, would they want this information and suggestions for presenting prognosis
PCP questionnaire (Appendix A7)	Email after the visit	- Each time: whether prognostic information was useful, helpful, & feedback on scripts - First time: assess facilitators and barriers to discussing prognosis when discussing stopping screening; PCP race/ethnicity, gender, practice characteristics
Chart abstraction (Appendix A8)	After note is signed in chart	- Abstract text from note that refers to cancer screening and/or patient prognosis - Research team will review text to assess if stopping screening/prognosis discussed

Impact: PCPs need strategies for communicating prognosis to older adults with <10 years life expectancy so that patients have the information they need and desire to make informed, valued-based medical decisions.

B. Statistical Considerations

Aim 1:

Analyses: We will use several methods for addressing rigor in qualitative research.^{72, 94} All interviews will be audio taped (using 2 audio recorders) and transcribed verbatim. Using thematic analysis,^{30,33} our inter-disciplinary team (Drs. [name], [name], [name], and [name]) will independently review transcripts from the first PCP and patient focus groups and the first three patient interviews to identify important concepts that emerge and to create a common codebook that will be used to code

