Data analyses: Our study is descriptive and exploratory. Since we recruited 94 women ≥ 75 years from 46 PCPs in the first year of our DA trial, we feel our recruitment goals are feasible. We will report how many PCPs found prognostic information useful and helpful, and facilitators and barriers to using prognostic information when discussing stopping cancer screening. Using chi-square tests, we will examine if PCP experiences differ by their sex or practice site (BIDMC/APG). With 45 PCPs we will have limited power for these analyses; however, we will explore if there is a direction of effect. We will also report how many patients reported that their PCP discussed stopping cancer screening and/or their prognosis and patients' perceptions of these discussions. We will use chi-square statistics to examine if there are differences in patient preferences or experiences by their sex, age, or practice site. For example, with 100 patients and assuming that 50% are female (n=45), at an alpha of 0.05, we will have 0.81 power to detect a 28% difference in preferences for prognostic discussions by patient sex. While we will have limited power to detect small differences in patient characteristics around preferences for prognostic information, we will examine if there is a direction of effect. We will also examine if patients' intentions to be screened (measured on a validated 15 point scale)⁹⁵ change after seeing their PCP using the Wilcoxon Signed Rank Test. In our decision aid trial, we have recruited 196 women ≥ 75 years with <10 year life expectancy. At baseline, their mean intentions to be screened with mammography on the 15 point scale was 3.7 (+/-4.9), indicating that on average they were strongly leaning towards being screened. Therefore, if we assume in this study that we will have at least 40 female participants with complete data (accounts for 5 women missing data) and that the within pair correlation is as low as 0.1 (however, we expect a higher degree of correlation and therefore higher power), we will have 0.87 power to tell a difference in a mean score of 3.7 before the PCP visit and a mean score of 7 (being unsure about screening among participants on average) after

the PCP visit if the standard deviation is also 4.9. In sensitivity analyses, we will examine if there is a clustering effect by PCP. We anticipate greater power to examine differences in intentions to be screened for CRC since both sexes are screened for CRC.

C. Subject Selection

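### The Aim 2 patient comparison by practice site uses a chi-square that ignores clustering by PCP, which modestly inflates its error rate; the planned clustering check names no method or outcomes

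*Combined protocol and SAP*

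**What the plan says.** The analysis is in section B3.B, Statistical Considerations, Aim 2, Data analyses. For patients: "We will use chi-square statistics to examine if there are differences in patient preferences or experiences by their sex, age, or practice site". For PCPs: "Using chi-square tests, we will examine if PCP experiences differ by their sex or practice site (BIDMC/APG"), so site is also used there as a characteristic of the PCP. The only provision for clustering is one sentence: "In sensitivity analyses, we will examine if there is a clustering effect by PCP". It follows the paragraph on change in screening intentions (Wilcoxon signed rank test) and names no model, variance estimator or outcomes.

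The design figures are in B3.A and B6:

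- The Overview says "We will give 45 PCPs (23 community-based) the scripts and patient prognostic information", with 1-3 patients per PCP and a goal of 100 patients. B1 also says 1-3, and B2 says up to 3.
- Aim 2, PCP recruitment, says "we will attempt to recruit up to 5 of their patients to participate", yet sends the PCP questionnaire after three patients. B6 also says up to 5 and sends it after the fifth.
- The community share is 23 of 45 in the Overview. In Aim 2, PCP recruitment, it is one third: "We aim to have 45 PCPs (1/3 community-based) participate".

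Table 2 opens the patient follow-up questionnaire with an item for everyone: "Whether PCP talked about stopping cancer screening and/or patient life expectancy". The later items branch. Satisfaction, feelings and feedback follow a yes; whether the patient would want the information follows a no.

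**The concern.** A Pearson chi-square assumes independent patients. Here patients are recruited through a participating PCP, and that PCP receives the scripts and the prognosis. Whether the PCP raised the subject is largely the PCP's own behaviour, so answers within a PCP are plausibly correlated. Such correlation matters most for a factor that does not vary within the cluster. Site is such a factor: the plan treats it as a PCP attribute, and Table 1 counts PCPs by site. That it is constant within a PCP is an inference from this structure, but nothing in the documents contradicts it.

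With positive correlation, the chi-square understates the variance of the site difference and its p-value is too small. A reader could then take an academic versus community difference as better supported than it is. The clustering check does not settle this. It may not reach the chi-square comparisons at all, and if it does, the unclustered p-value is still the one reported first.

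**Working it through.** **The plan's own figure.** The stated power of 0.81 for a 28-point difference by sex assumes independent patients. Taking 50 v 50 and rates of 36% and 64% (assumed; the plan gives no base rate), two-sided 0.05, no continuity correction:

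- SE under the null = sqrt(0.5 × 0.5 × 2/50) = 0.100; SE under the alternative = sqrt(2 × 0.36 × 0.64/50) = 0.096.
- Power = Φ((0.28 − 1.96 × 0.100)/0.096) = Φ(0.875) = 0.81.

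The figure reproduces with no allowance for clustering. It concerns sex, so it is not itself in question.

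**Design effect for site.** Mean cluster size is 100/45 = 2.22. The documents give neither the ICC nor the spread of cluster sizes, so both are assumed. For a factor fixed within a PCP with m patients:

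- DEFF = 1 + (Σm²/N − 1) × ICC; effective n = N/DEFF; approximate true error = 2 × (1 − Φ(1.96/√DEFF)).
- Illustrative 1-3 mix: 10 PCPs with 1 patient, 15 with 2, 20 with 3. N = 10 + 30 + 60 = 100; Σm² = 10 + 60 + 180 = 250; DEFF = 1 + 1.5 × ICC.
- Illustrative mix of up to 5: 20 PCPs with 1, 10 with 2, and 5 each with 3, 4 and 5. N = 20 + 20 + 15 + 20 + 25 = 100; Σm² = 20 + 40 + 45 + 80 + 125 = 310; DEFF = 1 + 2.1 × ICC.

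| ICC (assumed) | DEFF, 1-3 | Effective n | Error by formula | DEFF, up to 5 | Effective n | Error by formula |
|---|---|---|---|---|---|---|
| 0.05 | 1.075 | 93 | 5.9% | 1.105 | 90 | 6.2% |
| 0.10 | 1.15 | 87 | 6.8% | 1.21 | 83 | 7.5% |
| 0.20 | 1.30 | 77 | 8.6% | 1.42 | 70 | 10.0% |

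**Simulation, item asked of all patients.** Beta-binomial data with no site difference, 40,000 runs per cell, 23 or 15 community PCPs, true proportion 0.5 or 0.3. Ranges are over those four cells.

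| ICC (assumed) | Uncorrected, 1-3 | Uncorrected, up to 5 | Continuity-corrected, 1-3 |
|---|---|---|---|
| 0.05 | 5.9-6.6% | 6.3-6.8% | 3.5-4.2% |
| 0.10 | 6.6-7.3% | 7.4-8.0% | 4.1-4.8% |
| 0.20 | 8.5-9.1% | 10.1-10.5% | 5.4-6.2% |

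Repeat runs and other 1-3 mixes reached 7.7% at ICC 0.10 and 9.7% at 0.20. With sex assigned at random within PCP, the uncorrected test stayed at 4.9-5.6%.

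**Simulation, branched items.** The 1-3 mix with half the patients in a branch (assumed) and branch membership clustered at the same ICC. Uncorrected error was 5.5-5.7% at ICC 0.05, 5.9-6.3% at 0.10 and 6.9-7.7% at 0.20. The continuity-corrected test did not exceed 5%. Fewer patients per PCP means a smaller design effect.

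**The alternative test.** A logistic GEE score test with PCP as cluster, independence working correlation and variance factor K/(K − 1), K being the number of PCPs, rejected at 4.7-5.2% for ICCs from 0 to 0.30, with correlation at PCP level only (up to about 5.4% in repeat runs). With a small practice-level variance added (0.02 on the latent probit scale, PCP-level 0.10, two BIDMC practices and 8 or 16 community practices, all assumed), it rejected at about 8%.

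**The case against.** The strongest reply is that the plan calls Aim 2 descriptive and exploratory, concedes limited power, looks for direction of effect, and already intends to examine clustering by PCP. Clusters are small, no decision rest on a site p-value, and alpha 0.05 is cited only in the sex example. All of this is true and lowers the severity. It does not give the unclustered p-value the error rate that it appears to have.

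Three limits on size also stand. The larger figures apply only to the item put to every patient; the branched items are less affected. With a continuity correction, even the all-patient item exceeds 5% only from an ICC somewhere between 0.10 and 0.20 with 1-3 patients per PCP, and the plan does not say which version is meant. The mix of up to 5 is illustrative, and several sections limit the number to 3. The feasibility figure ("Since we recruited 94 women ≥ 75 years from 46 PCPs in the first year of our DA trial") gives a mean of 94/46 = 2.04 patients per PCP, but it comes from another trial and says nothing about the spread.

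The power cost is real too. Against the uncorrected chi-square, for a 28-point site difference, the score test loses 2-6 points of power with no clustering and 6-12 at ICC 0.10. Under clustering, part of what is lost is power that the chi-square gains only through its inflated error.

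A reader might infer that the plan overlooks clustering, that all its chi-square tests are invalid, or that the 0.81 power is overstated. The documents support none of these: clustering is mentioned, sex varies within a PCP, and the 0.81 is for sex.

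**Conclusion.** The point holds and is minor. Under positive within-PCP correlation, the uncorrected chi-square by site has a true error of about 6%, 7% or 9% at an ICC of 0.05, 0.10 or 0.20 for the all-patient item with 1-3 patients per PCP, and somewhat more if up to 5 are recruited. For the branched items it is about 5.5%, 6% or 7%. This rests on assumed ICCs, assumed cluster-size mixes, half the patients per branch, and site being constant within a PCP.

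It would go too far to say that the error rate doubles across the patient outcomes, since rates near 10% need a high assumed ICC or larger clusters and the all-patient item. It would also go too far to say that a PCP-clustered test makes the site comparison sound. That test does not remove correlation between PCPs in the same practice, and the documents describe two BIDMC practices and up to 16 community ones. Site p-values remain exploratory under either test.

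**What to change.** In B3.B, Aim 2, for patient-level comparisons by practice site, report a PCP-clustered test as the main p-value, for example a logistic GEE score test with PCP as cluster and the K/(K − 1) factor. Keep the plain chi-square by site as the sensitivity analysis. A Rao-Scott test with an F reference on PCP-based degrees of freedom is a second choice, with less tight error in the same simulations (4.8-6.5%). Leave the comparisons by sex and age as planned. State which outcomes the clustering check covers, including whether it extends to the change in screening intentions and by what method, and whether the chi-square is continuity-corrected. Add that practice-level correlation is not removed. Reconciling the patients per PCP (3 or 5) and the community share (23 of 45 or one third) would fix the inputs on which the size depends.

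The cost is two or three sentences and a little programming; each patient is already tied to a PCP, so no new data are needed. Site p-values will be larger and nominal power lower, as set out above.

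### Table 2 lists the preference-for-prognosis item only for patients whose PCP did not raise the topic, but the 0.81 power for a sex difference in that preference is stated for 100 patients; separately, 100, 50% female and n=45 do not agree

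*Combined protocol and SAP*

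**What the plan says.** Section B3.B (Statistical Considerations, Aim 2, Data analyses) plans chi-square tests of "differences in patient preferences or experiences by their sex, age, or practice site". It illustrates them with a power figure: "we will have 0.81 power to detect a 28% difference in preferences for prognostic discussions by patient sex". The sample and test level behind that figure are given as "with 100 patients and assuming that 50% are female (n=45), at an alpha of 0.05". No base rate is given.

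Table 2 in Section B3.A is the only place in the available text that lists the Aim 2 patient items. Its follow-up row starts with a screening question: "Whether PCP talked about stopping cancer screening and/or patient life expectancy". Patients who answer yes are listed for satisfaction, feelings and feedback. The rest get "If not, would they want this information and suggestions for presenting prognosis". The background-questionnaire row has no item on wanting prognostic information. The Overview in Section B3.A describes the follow-up only in general terms: "We will interview patients after each visit to learn from their perspective if their PCP discussed their prognosis and/or stopping cancer screening".

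The next power statement in Section B3.B, on screening intentions, assumes "at least 40 female participants with complete data (accounts for 5 women missing data".

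**The concern.** The power statement counts every patient, while the only listed item that measures wanting prognostic information goes to one branch. If the questionnaire works as printed, the denominator is the patients with no discussion, and there are fewer than 100 of them.

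The issue goes beyond precision. Section B5 treats discussing prognosis as the PCP's choice, and in Aim 2 that choice comes after the PCP has received the scripts and the patient's prognosis. The subset would therefore be formed after the intervention and would shrink as the scripts are used more. It would describe only patients whose PCP stayed silent. If PCPs raise the topic at different rates by patient sex, age or site, the groups compared would also be selected differently. Answers that were never requested cannot be recovered in the analysis.

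The second matter is arithmetic: 100 patients, 50% female and 45 women cannot all be true.

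**Working it through.** **Inputs.** From Section B3.B: 100 patients, 50% female, n=45, alpha 0.05, a 28-point difference, chi-square test. Assumptions: a two-sided test, and base rates, which the plan does not state. I use pairs from 36% v 64% (centred on 50%, close to the lowest power for a 28-point gap) to 60% v 88%. The background (B.2) cites about 60% of older adults wanting this information in general settings and 52% in the screening context.

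**Formula.** For a two-proportion test with pooled variance, power = Φ[(d − 1.96·s0)/s1]. Here s0 = √[p̄(1−p̄)(1/n1+1/n2)], s1 = √[p1(1−p1)/n1 + p2(1−p2)/n2] and d = 0.28.

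**Reproducing 0.81.** With 50 per sex and 36% v 64%:
- s0 = √(0.25 × 0.04) = 0.100
- s1 = √(2 × 0.2304/50) = 0.096
- (0.28 − 0.196)/0.096 = 0.875, so power = 0.809

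The stated figure is reproduced, with the whole sample as denominator.

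**Restricting to patients with no discussion.** If a share r of patients had the discussion, equally in both sexes, each group has 50(1−r) patients:

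| Share with discussion | n per sex | 36% v 64% | 50% v 78% | 60% v 88% |
|---|---|---|---|---|
| 0% | 50 | 0.809 | 0.841 | 0.903 |
| 5% | 47.5 | 0.788 | 0.822 | 0.888 |
| 20% | 40 | 0.715 | 0.751 | 0.827 |
| 50% | 25 | 0.508 | 0.543 | 0.623 |

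With rates centred on 50%, the difference detectable at 0.81 power rises from 28 points (50 per sex) to 39 points (25 per sex).

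The documents give no discussion rate for Aim 2. The nearest figure is the background statement (B.1) that under 5% of older adults report having discussed stopping screening. That predates any intervention and concerns stopping screening rather than prognosis.

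**The count of women.** 50% of 100 is 50. The later statement gives 40 complete + 5 missing = 45, and 45/0.50 = 90 patients. Power for 28 points under each reading:

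| Women/men | 36% v 64% | 52% v 80% |
|---|---|---|
| 50/50 | 0.809 | 0.851 |
| 45/55 | 0.805 | 0.850 |
| 45/45 | 0.766 | 0.811 |

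Both 50/50 at 36% v 64% and 45/45 at 52% v 80% give 0.81, so the figure cannot show whether 100 or 90 patients were used.

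**The case against.** The strongest reply is that Table 2 is a summary and is demonstrably incomplete. The plan tests whether screening intentions "change after seeing their PCP using the Wilcoxon Signed Rank Test", which needs a post-visit intention item, and the follow-up row does not list one. A table that omits one required item is weak evidence that another is withheld from some patients. Appendix A6 decides the matter and was not available. This stands, and it is why the point is conditional. The same omission is also a reason to bring Table 2 and A6 into line.

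Section B3.B also never says which item is the preference variable. The trigger joins two topics with and/or, so a patient whose PCP raised screening but not life expectancy might still be asked. This stands too, and it calls for naming the item and the trigger.

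The plan describes Aim 2 as exploratory, offers the calculation as an illustration and concedes limited power for small differences. That limits the severity but leaves the denominator unsettled.

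Asking satisfaction of those who had the talk and wishes of those who did not is a reasonable design, and a preference voiced after a discussion may be coloured by it. That supports showing results by discussion status. It does not support leaving one group unasked while quoting power for everyone.

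A reader might infer that the 0.81 is miscalculated, or that the comparison is certainly underpowered. Neither is supported: 0.81 reproduces, and at 60% v 88% power is still 0.83 with 20% discussed. No single discussion rate marks the fall below 0.80, because that point moves with the unstated base rate; at 50% v 78% it is about 10%.

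**Conclusion.** The point holds for Table 2 as printed and is minor. The documents list the preference item for one branch only and state its power for 100 patients. If A6 follows Table 2, the comparisons by sex, age and site rest on a subset chosen by PCP behaviour. The loss could be negligible (0.79 to 0.89 with 5% discussed) or substantial (0.51 to 0.62 with 50% discussed). These figures assume a two-sided 0.05 test, 50 per sex before restriction, equal discussion rates in both sexes, complete data and the base rates shown. If A6 already asks everyone, only Table 2, the counts and the missing base rate need correcting.

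The count of women is inconsistent, but the effect is small: 0.809 against 0.805 if 45 of 100 are women. It is larger only if 90 patients were meant, and then it depends on the base rate (0.77 at 36% v 64%, 0.81 at 52% v 80%). A reader might conclude that 45 is simply a slip for 50. The documents do not settle that: 45 fits the later count of 40 plus 5, so the 100 may be the figure out of line.

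**What to change.** 1. Ask every patient the preference item at follow-up, with wording suited to those who did and did not have the discussion. Make Table 2 and Appendix A6 both say so.
2. Name that item in Section B3.B as the preference variable. Report it by sex, age and site overall, and by discussed or not discussed.
3. If the branch is kept, state exactly what triggers it, restate the power for the not-discussed subset over a range of discussion rates, and limit the conclusion to that subset.
4. Reconcile 100, 50% and 45 in both power statements, and state the base rate actually used.

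The cost is one existing item put to all patients in two wordings, plus edits to Table 2, A6 and the two power statements. The downside is that a preference given after a discussion may be influenced by it; reporting by discussion status makes that visible. The change in who is asked has to be made before follow-up data are collected.
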